## **6.5. Dose Modification**

Not applicable.

## **6.6. Continued Access to Study Intervention After the End of the Study**

No intervention will be provided to study participants at the end of their study participation.

## **6.7. Treatment of Overdose**

For this study, any dose of PF-07304814 greater than 700 mg within a 24-hour time period will be considered an overdose.

There is no specific treatment for an overdose.

In the event of an overdose, the investigator should:

1. Contact the medical monitor within 24 hours.
2. Closely monitor the participant for any AEs/SAEs and laboratory abnormalities for at least 5 half-lives or 28 calendar days after the overdose of PF-07304814 (whichever is longer).
3. Document the quantity of the excess dose as well as the duration of the overdose in the CRF.
4. Overdose is reportable to Pfizer Safety **only when associated with an SAE**.
5. Obtain a blood sample for PK analysis within 1 day from the date of the last dose of study intervention if requested by the medical monitor (determined on a case-by-case basis).

## **6.8. Concomitant Therapy**

Use of prescription or nonprescription drugs and dietary and herbal supplements are prohibited within 7 days or 5 half-lives (whichever is longer) prior to the first dose of study intervention. Limited use of nonprescription medications that are not believed to affect participant safety or the overall results of the study may be permitted on a case-by-case basis following approval by the sponsor. Acetaminophen/paracetamol may be used at doses of  $\leq 1$  g/day. If an individual participant has not experienced a bowel movement within 36 hours of their previous bowel movements, administration of a mild laxative (eg, prune juice or a mild stool softener) may be used, with the goal to facilitate at least 1 daily bowel movement.

Use of strong CYP3A inhibitors and/or inducers within 28 days or 5 half-lives (whichever is longer) prior to the first dose of investigational product or during the study are prohibited.

All concomitant treatments taken during the study must be recorded with indication, daily dose, and start and stop dates of administration. All participants will be questioned about concomitant treatment at each clinic visit.

Treatments taken within 28 days before the first dose of study intervention will be documented as a prior treatment. Treatments taken after the first dose of study intervention will be documented as concomitant treatments.

### **6.8.1. Rescue Medicine**

There is no rescue therapy to reverse the AEs observed with PF-07304814; standard medical supportive care must be provided to manage the AEs.

## **7. DISCONTINUATION OF STUDY INTERVENTION AND PARTICIPANT DISCONTINUATION/WITHDRAWAL**

### **7.1. Discontinuation of Study Intervention**

It may be necessary for a participant to permanently discontinue study intervention (definitive discontinuation). Reasons for discontinuation of study intervention include (but are not limited to) the following: AEs, Physician decision, withdrawal by participants.

If study intervention is definitively discontinued, the participant will not remain in the study for further evaluation. See the [SoA](#) for data to be collected at the time of discontinuation of study intervention.

### **7.1.1. ECG Changes**

A participant who meets either bulleted criterion on a single ECG will have 2 additional ECGs measured and the average of the triplicate ECG readings recorded. If the average of triplicate ECG readings meets either of the bulleted criterion, the participant will be withdrawn from the study intervention after consultation with the investigator and sponsor.

- QTcF >500 msec.
- Change from baseline: QTcF >60 msec and QTcF >450 msec.

If a clinically significant finding is identified (including, but not limited to, changes from baseline in QTcF after enrollment), the investigator or qualified designee will determine if the participant can continue in the study and if any change in participant management is needed. This review of the ECG printed at the time of collection must be documented. Any new clinically relevant finding should be reported as an AE.

## **7.2. Participant Discontinuation/Withdrawal From the Study**

A participant may withdraw from the study at any time at his/her own request. Reasons for discontinuation from the study include the following:

- Refused further study procedures;
- Lost to follow-up;
- Death;
- Study terminated by sponsor;

At the time of discontinuing from the study, if possible, an early discontinuation visit should be conducted. See the [SoA](#) for assessments to be collected at the time of study discontinuation and follow-up and for any further evaluations that need to be completed.

If a participant withdraws from the study, he/she may request destruction of any remaining samples taken and not tested, and the investigator must document any such requests in the site study records and notify the sponsor accordingly.

If the participant withdraws from the study and also withdraws consent (see Section 7.2.1) for disclosure of future information, no further evaluations should be performed and no additional data should be collected. The sponsor may retain and continue to use any data collected before such withdrawal of consent.

### **7.2.1. Withdrawal of Consent**

Participants who request to discontinue receipt of study intervention will remain in the study and must continue to be followed for protocol-specified follow-up procedures. The only exception to this is when a participant specifically withdraws consent for any further contact with him or her or persons previously authorized by the participant to provide this information. Participants should notify the investigator in writing of the decision to withdraw consent from future follow-up, whenever possible. The withdrawal of consent should be explained in detail in the medical records by the investigator, as to whether the withdrawal is only from further receipt of study intervention or also from study procedures and/or posttreatment study follow-up, and entered on the appropriate CRF page. In the event that vital status (whether the participant is alive or dead) is being measured, publicly available information should be used to determine vital status only as appropriately directed in accordance with local law.

### **7.3. Lost to Follow up**

A participant will be considered lost to follow-up if he or she repeatedly fails to return for scheduled visits and is unable to be contacted by the study site.

The following actions must be taken if a participant fails to attend a required study visit:

- The site must attempt to contact the participant and reschedule the missed visit as soon as possible. Counsel the participant on the importance of maintaining the assigned visit schedule and ascertain whether the participant wishes to and/or should continue in the study;
- Before a participant is deemed lost to follow-up, the investigator or designee must make every effort to regain contact with the participant (where possible, 3 telephone calls and, if necessary, a certified letter to the participant's last known mailing address or local equivalent methods). These contact attempts should be documented in the participant's medical record;
- Should the participant continue to be unreachable, he/she will be considered to have withdrawn from the study.

## 8. STUDY ASSESSMENTS AND PROCEDURES

The investigator (or an appropriate delegate at the investigator site) must obtain a signed and dated ICD before performing any study-specific procedures.

Study procedures and their timing are summarized in the [SoA](#). Protocol waivers or exemptions are not allowed.

Safety issues should be discussed with the sponsor immediately upon occurrence or awareness to determine whether the participant should continue or discontinue study intervention.

Adherence to the study design requirements, including those specified in the [SoA](#), is essential and required for study conduct.

All screening evaluations must be completed and reviewed to confirm that potential participants meet all eligibility criteria. The investigator will maintain a screening log to record details of all participants screened and to confirm eligibility or record reasons for screening failure, as applicable.

Participants will be screened within 42 days prior to administration of the study intervention to confirm that they meet the study population criteria for the study. If the time between screening and dosing exceeds 42 days as a result of unexpected delays (eg, delayed drug shipment), then participants do not require rescreening if the laboratory results obtained prior to first dose administration meet eligibility criteria.

A participant who qualified for this protocol but did not enroll from an earlier cohort/group may be used in a subsequent cohort/group without rescreening, provided laboratory results obtained prior to the first dose administration meet eligibility criteria for this study. In addition, other clinical assessments or specimen collections, eg, retained research sample, may be used without repeat collection, as appropriate.

Every effort should be made to ensure that protocol-required tests and procedures are completed as described. However, it is anticipated that from time to time there may be circumstances outside the control of the investigator that may make it unfeasible to perform the test. In these cases, the investigator must take all steps necessary to ensure the safety and well-being of the participant. When a protocol-required test cannot be performed, the investigator will document the reason for the missed test and any corrective and preventive actions that he or she has taken to ensure that required processes are adhered to as soon as possible. The study team must be informed of these incidents in a timely manner.

If an IV catheter is utilized for blood sample collections, ECGs and vital sign assessments (pulse rate and BP) should be collected prior to the insertion of the catheter. Blood samples for PK must not be taken from the same arm used for IV drug administration on the day of drug infusion.

For samples being collected and shipped, detailed collection, processing, storage, and shipment instructions and contact information will be provided to the investigator site prior to initiation of the study.

The total blood sampling volume for individual participants in this study is approximately 280 mL rounded up to nearest 5 mL. The actual collection times of blood sampling may change. Additional blood samples may be taken for safety assessments at times specified by Pfizer, provided the total volume taken during the study does not exceed 500 mL during any period of 56 consecutive days.

To prepare for study participation, participants will be instructed on the information in the Lifestyle Considerations and Concomitant Therapy sections of the protocol.

## **8.1. Efficacy Assessments**

Not applicable.

## **8.2. Safety Assessments**

Planned time points for all safety assessments are provided in the [SoA](#). Unscheduled clinical laboratory measurements may be obtained at any time during the study to assess any perceived safety issues.

### **8.2.1. Physical Examinations**

A complete physical examination will include, at a minimum, head, ears, eyes, nose, mouth, skin, heart and lung examinations, lymph nodes, and gastrointestinal, musculoskeletal, and neurological systems.

A brief physical examination will include, at a minimum, assessments of general appearance, the respiratory and cardiovascular systems, and participant-reported symptoms.

Physical examinations may be conducted by a physician, trained physician's assistant, or nurse practitioner as acceptable according to local regulation.

Height and weight will also be measured and recorded as per the [SoA](#). For measuring weight, a scale with appropriate range and resolution is used and must be placed on a stable, flat surface. Participants must remove shoes, bulky layers of clothing, and jackets so that only light clothing remains. They must also remove the contents of their pockets and remain still during measurement of weight.

Physical examination findings collected during the study will be considered source data and will not be required to be reported, unless otherwise noted. Any untoward physical examination findings that are identified during the active collection period and meet the definition of an AE or SAE ([Appendix 3](#)) must be reported according to the processes in [Sections 8.3.1 to 8.3.3](#).

### **8.2.2. Vital Signs**

Supine BP will be measured with the participant's arm supported at the level of the heart, and recorded to the nearest mmHg after approximately 5 minutes of rest. The same arm (preferably the dominant arm) will be used throughout the study. BP should not be taken from the arm with an intravenous infusion (even if that is the dominant arm). Participants should be instructed not to speak during measurements.

The same properly sized and calibrated BP cuff will be used to measure BP each time. The use of an automated device for measuring BP and pulse rate is acceptable; however, when done manually, pulse rate will be measured in the brachial/radial artery for at least 30 seconds. When the timing of these measurements coincides with a blood collection, BP and pulse rate should be obtained prior to the nominal time of the blood collection.

Additional collection times, or changes to collection times, of BP and pulse rate will be permitted, as necessary, to ensure appropriate collection of safety data.

#### **8.2.2.1. Temperature**

Temperature will be measured orally. No eating, drinking, or smoking is allowed for 15 minutes prior to the measurement.

### **8.2.3. Electrocardiograms**

Standard 12-lead ECGs utilizing limb leads (with a 10 second rhythm strip) should be collected at times specified in the [SoA](#) section of this protocol using an ECG machine that automatically calculates the heart rate and measures PR, QT, and QTcF intervals and QRS complex. Alternative lead placement methodology using torso leads (eg, Mason-Likar) should not be used given the potential risk of discrepancies with ECGs acquired using standard limb lead placement. All scheduled ECGs should be performed after the participant has rested quietly for at least 5 minutes in a supine position.

To ensure safety of the participants, a qualified individual at the investigator site will make comparisons to baseline measurements. Additional ECG monitoring will occur if a) a postdose QTcF interval is increased by  $>60$  msec from the baseline **and** is  $>450$  msec; or b) an absolute QTcF value is  $>500$  msec for any scheduled ECG. If either of these conditions

occurs, then 2 additional ECGs will be collected approximately 2 to 4 minutes apart and the average of the 3 taken to confirm the original measurement. If the QTcF values from these repeated ECGs remain above the threshold value, then the participant will be withdrawn.

If a) a postdose QTcF interval remains >60 msec from the baseline **and** is >450 msec; or b) an absolute QT value is >500 msec for any scheduled ECG for greater than 4 hours (or sooner, at the discretion of the investigator); or c) QTcF intervals get progressively longer, the participant should undergo continuous ECG monitoring. A cardiologist should be consulted if QTcF intervals do not return to less than the criteria listed above after 8 hours of monitoring (or sooner, at the discretion of the investigator).

In some cases, it may be appropriate to repeat abnormal ECGs to rule out improper lead placement as contributing to the ECG abnormality. It is important that leads be placed in the same positions each time in order to achieve precise ECG recordings. If a machine-read QTc value is prolonged, as defined above, repeat measurements may not be necessary if a qualified medical provider's interpretation determines that the QTcF values are in the acceptable range.

ECG values of potential clinical concern are listed in [Appendix 7](#).

#### **8.2.4. Clinical Safety Laboratory Assessments**

See [Appendix 2](#) for the list of clinical safety laboratory tests to be performed and the **SoA** for the timing and frequency. All protocol-required laboratory assessments, as defined in [Appendix 2](#), must be conducted in accordance with the laboratory manual and the **SoA**. Unscheduled clinical laboratory measurements may be obtained at any time during the study to assess any perceived safety issues.

The investigator must review the laboratory report, document this review, and record any clinically relevant changes occurring during the study in the AE section of the CRF. Clinically significant abnormal laboratory findings are those which are not associated with the underlying disease, unless judged by the investigator to be more severe than expected for the participant's condition.

All laboratory tests with values considered clinically significantly abnormal during participation in the study or within 5 days after the last dose of study intervention should be repeated until the values return to normal or baseline or are no longer considered clinically significant by the investigator or medical monitor.

If such values do not return to normal/baseline within a period of time judged reasonable by the investigator, the etiology should be identified and the sponsor notified.

See [Appendix 6](#) for suggested actions and follow-up assessments in the event of potential drug-induced liver injury.

### **8.2.5. COVID-19 specific assessments**

Participants will be tested for SARS-COVID-19 infection by RT-PCR prior to being admitted to the clinic for confinement and a subsequent COVID-19 test will be performed after approximately 4 days (ie, upon completion of  $4 \times 24$  hours in house), or if they develop COVID-19 like symptoms. Additional testing may be required by local regulations or by the principal investigator.

## **8.3. Adverse Events, Serious Adverse Events, and Other Safety Reporting**

The definitions of an AE and an SAE can be found in [Appendix 3](#).

AEs may arise from symptoms or other complaints reported to the investigator by the participant (or, when appropriate, by a caregiver, surrogate, or the participant's legally authorized representative), or they may arise from clinical findings of the Investigator or other healthcare providers (clinical signs, test results, etc.).

The investigator and any qualified designees are responsible for detecting, documenting, and recording events that meet the definition of an AE or SAE and remain responsible to pursue and obtain adequate information both to determine the outcome and to assess whether the event meets the criteria for classification as an SAE or caused the participant to discontinue the study intervention (see [Section 7.1](#)).

During the active collection period as described in Section 8.3.1, each participant will be questioned about the occurrence of AEs in a nonleading manner.

In addition, the investigator may be requested by Pfizer Safety to obtain specific follow-up information in an expedited fashion.

### **8.3.1. Time Period and Frequency for Collecting AE and SAE Information**

The time period for actively eliciting and collecting AEs and SAEs (“active collection period”) for each participant begins from the time the participant provides informed consent, which is obtained before the participant’s participation in the study (ie, before undergoing any study-related procedure and/or receiving study intervention), through and including a minimum of 28 calendar days, except as indicated below, after the last administration of the study intervention.

Follow-up by the investigator continues throughout and after the active collection period and until the AE or SAE or its sequelae resolve or stabilize at a level acceptable to the investigator.

For participants who are screen failures, the active collection period ends when screen failure status is determined.

If the participant withdraws from the study and also withdraws consent for the collection of future information, the active collection period ends when consent is withdrawn.

If a participant permanently discontinues or temporarily discontinues study intervention because of an AE or SAE, the AE or SAE must be recorded on the CRF and the SAE reported using the CT SAE Report Form.

Investigators are not obligated to actively seek information on AEs or SAEs after the participant has concluded study participation. However, if the investigator learns of any SAE, including a death, at any time after a participant has completed the study, and he/she considers the event to be reasonably related to the study intervention, the investigator must promptly report the SAE to Pfizer using the CT SAE Report Form.

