Blood sample for unlabeled PF-07304814 & PF-00835231 PK o			X	X	X	X	X	X	X	X	X	X	X	X	X	X	X	X	X	X	
Blood sample for metabolite profiling p		X		X			X		X				X		X			X			
Fecal collection q		X → X		0-24 hour						24-48 hour				48-72 hour	72-96 hour	96-120 hour	120-144, 144-168, 168-192, and 192-216 hour				
Urine collection r			X	0-24 hour						24-48 hour				48-72 hour	72-96 hour	96-120 hour	120-144, 144-168, 168-192, and 192-216 hour				
Retained Research Sample for Genetics (Prep D1) s		X																			
CRU discharge																		X			
Serious and nonserious AE monitoring	X	→	→	→	→	→	→	→	→	→	→	→	→	→	→	→	→	→	X	X	

- Day relative to start of study intervention (Day 1).
- Participants will be admitted to the clinic on Day -1. Participants will be discharged on Day 10 following the final assessments.
- Medical history will include a history of prior illegal drug, alcohol, and tobacco use, as well as blood donation within prior 60 days. Medical history will be recorded at Screening and updated on Day -1.
- A complete physical exam (PE), without genitourinary evaluation will be performed by trained medical personnel at the investigator site at Screening or Day -1 (height and weight must be obtained at Screening to obtain BMI for eligibility criteria) and on Day 10 prior to discharge. A brief PE may be performed at other designated time points at the discretion of the investigator.

Visit Identifier a Abbreviations used in this table may be found in Appendix 8 .	Screening	Study Period														Follow-Up	Early Termination/ Discontinuation				
		Day -42 to Day -2	Day -1	Day 1						Day 2			Day 3	Day 4	Day 5	Day 6	Day 7	Day 10	28-35 Days b		
Hours After Start of Infusion				predose	0	0.5	1	2	6	12	24	25	27	32	48	72	96	120	144	216	

- e. Safety laboratory assessments including urinalysis, hematology, and chemistry will be performed at the indicated time-points. All the safety laboratory samples must be collected following at least a 4 hour fast. Additional safety laboratory assessments may be performed at any time at the discretion of the investigator.
- f. Demographics will include participant race, ethnicity, age, and gender during the screening visit.
- g. Participants will be counselled regarding contraception requirements on Screening, Day -1, and Follow-up.

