- q. Each bowel movement starting from the time of dosing must be collected at the time of passing while the subject is confined in the clinic. Date, and time must be recorded. A fecal sample from Day -1 to Day 1 prior to dosing (feces “blank”), if possible. If an individual subject has not experienced a bowel movement within 36 hours of their previous bowel movements, fluid intake should be increased and administration of a mild laxative (eg, prune juice or a mild stool softener) should be implemented, with the goal to facilitate at least 1 daily bowel movement. The use of the laxative should be recorded.
- r. Urine samples will be collected daily through the morning of discharge. Each urine void must be collected. Each participant will empty his/her bladder prior to dosing, and a 10 mL aliquot from this urine (urine “blank”) will be retained. Postdose urine samples will be collected at voiding and labeled for the appropriate 24-hour time period in which each sample has been collected. At the end of each urine collection period, the total weight will be measured and recorded.

Visit Identifier a Abbreviations used in this table may be found in Appendix 8 .	Screening	Study Period														Follow-Up	Early Termination/ Discontinuation				
		Day -42 to Day -2	Day -1	Day 1						Day 2			Day 3	Day 4	Day 5	Day 6	Day 7	Day 10	28-35 Days t		
Hours After Start of Infusion				predose	0	0.5	1	2	6	12	24	25	27	32	48	72	96	120	144	216	

- s. Prep D1 Retained Research Samples for Genetics: If not collected on the designated collection day, collect at the next available time point when biospecimens are being collected in conjunction with a participant visit.
- t. A safety follow-up call will be made to participants 28 to 35 days from administration of the dose of study intervention.

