6.2. Safety Endpoints

An adverse event will be considered a Treatment-Emergent Adverse Event (TEAE) if the event started during the effective duration of treatment. All events that start on or after the first dosing day and time/ start time, if collected, but before the last dose plus the lag time (28 days) will be flagged as TEAEs. The algorithm will not consider any events that started prior to the first dose date. Any events occurring following start of treatment or increasing in severity will be counted as treatment emergent.

Events that occur in a non-treatment period (for example, Follow-up) will be counted as treatment emergent and attributed to the previous treatment taken.

The following data are considered in standard safety summaries (see protocol for collection days and list of parameters):

- *adverse events,*
- *laboratory data,*
- *vital signs data,*
- *ECG results.*

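### The 28-day minimum of active AE collection is not guaranteed for a participant whose infusion is stopped early, because Protocol 7.1 conflicts with 8.3.1 and 7.2.1

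*Protocol*

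**What the plan says.** **Collection period.** Protocol 8.3.1 starts active AE and SAE collection for each participant at consent and continues it "through and including a minimum of 28 calendar days, except as indicated below, after the last administration of the study intervention". Two paragraphs below then say expressly when the period ends sooner: at screen failure, and when consent to further information is withdrawn. The paragraph on stopping study intervention because of an AE asks only that the event be recorded and any SAE reported; it does not end collection. The section closes with: "Investigators are not obligated to actively seek information on AEs or SAEs after the participant has concluded study participation".

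**Early stop.** Protocol 7.1: "Reasons for discontinuation of study intervention include (but are not limited to) the following: AEs, Physician decision, withdrawal by participants". It continues: "If study intervention is definitively discontinued, the participant will not remain in the study for further evaluation". It refers to the Schedule of Activities (SoA) for the data due at discontinuation, and the SoA has an early-termination column that includes AE monitoring.

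**Participant-requested stop.** Protocol 7.2.1: "Participants who request to discontinue receipt of study intervention will remain in the study and must continue to be followed for protocol-specified follow-up procedures".

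**Post-discharge contact.** The only scheduled contact after Day 10 is in SoA footnote t: "A safety follow-up call will be made to participants 28 to 35 days from administration of the dose of study intervention". The infusion lasts 24 hours, and SoA footnote a counts study days from its start.

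**Analysis.** SAP 5.3 puts everyone who receives at least one dose in the safety set. SAP 6.2 says events that start on or after dosing "but before the last dose plus the lag time (28 days) will be flagged as TEAEs".

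**The concern.** Read together, 7.1 and the last paragraph of 8.3.1 allow a site to stop looking for AEs in a dosed participant well before the minimum that 8.3.1 sets. Under 7.1 the participant leaves the study. Once participation has concluded, 8.3.1 no longer requires the investigator to look. Section 7.2.1 does not repair this: it covers only participants who themselves ask to stop, not those stopped for an AE or by a physician, and even for that group it contradicts 7.1.

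TEAEs are a secondary endpoint, and the study has about 5 participants. The case is also foreseen. Protocol 2.3.1 names infusion-site reactions and thromboemboli as potential risks and says treatment may need to be discontinued if the infusion is not tolerated. A participant stopped for such a reason matters for the tolerability summary, and the SAP would carry that participant with a 28-day TEAE window that may not have been observed. The SAP text states no rule for truncated AE follow-up.

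A smaller question is whether the 28 days run from the start or the end of the 24-hour infusion. Footnote t, 8.3.1 and the SAP each leave this open.

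**Working it through.** **1. The plan's own figure.** The only stated figure that uses the call window is the total duration of approximately up to 11 weeks (Protocol 1.1 and 4.1).

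- Call counted from infusion start: 42 days of screening + 35 = 77 days; 77/7 = 11.0 weeks. The figure reproduces.
- Call counted from infusion end: 42 + 1 + 35 = 78 days; 78/7 = 11.1 weeks.

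Both round to 11 weeks, so the stated duration does not settle the anchor.

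**2. Who is covered after an early stop.**

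| Reason for stopping | 7.1 | 7.2.1 | 8.3.1 |
|---|---|---|---|
| AE | Leaves the study | Silent | Period not shortened |
| Physician decision | Leaves the study | Silent | Period not shortened |
| Participant asks to stop, consent kept | Leaves the study | Stays and is followed | Period not shortened |
| Consent to further information withdrawn | Leaves the study | Exception allowed | Period ends |

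The sections agree only in the last row.

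**3. What is kept and what can be lost.** The triggering AE must be recorded (8.3.1) and pursued to resolution, stabilization or another explanation (8.3.3). AEs are collected at early termination (SoA). SAP 8.3.3 summarizes discontinuations due to AEs. What remains exposed is active elicitation of new events after the early-termination visit.

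**4. Size.** Planned post-dose collection is 5 participants × 28 days = 140 person-days. One participant stopped early can lose up to about 28 of these: 28/140 = 20%.

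**5. How likely such a stop is.** The documents give no rate for this study. With an assumed per-participant probability p, the chance of at least one stop among 5 is 1 − (1 − p)^5.

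| Assumed p | At least one of 5 |
|---|---|
| 1% | 4.9% |
| 5% | 22.6% |
| 10% | 41.0% |
| 18.1% | 63.2% |

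The last row is the one-sided 95% upper bound for 0 of 15, that is 1 − 0.05^(1/15) = 0.181. It uses the earlier healthy-participant study in Protocol 2.2.4.1, which had 15 participants evaluable for safety and no discontinuations due to AEs. That count may include placebo exposure, so the bound is rough.

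**6. The anchor.** Take a full 24-hour infusion and a call 28 to 35 days later, which gives 8 nominal call days.

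- Counted from infusion start, the call falls 28 − 1 = 27 to 35 − 1 = 34 days after infusion end. Only the earliest of the 8 days is short, by 1 day: 1/28 = 3.6%.
- Counted from infusion end, the call falls 28 to 35 days after infusion end, with no shortfall.

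A shortened infusion narrows the start-to-end gap, so this item and the early-stop item do not add up.

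**The case against.** The best defence is that 8.3.1 is the section specific to AE collection, applies to each participant, and deals with stopping for an AE without shortening the period. Section 7.2 refers sites to the SoA for follow-up and any further evaluations after study discontinuation, and bars further data collection only when consent is also withdrawn. Footnote t promises the call to participants, not to completers alone. A careful site could therefore collect AEs for 28 days after an early stop. That reading is available, but none of these passages clearly overrides the flat statement in 7.1.

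One could also argue that the closing sentence of 8.3.1 on concluded participation is itself one of the exceptions. Unlike the paragraphs on screen failure and consent, it does not say that the collection period ends. If it did, the 28 days would no longer be a minimum.

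Parts of the defence do stand, and they rule out stronger readings that a reader might infer:

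- *That the minimum is not delivered at all.* A participant who completes the infusion gets the full 28 days on at least 7 of the 8 permitted call days.
- *That the most informative event is lost.* The AE that stops the infusion is recorded and followed.
- *That TEAE incidence is biased downward because unobserved time counts as event-free.* The SAP does not say this. SAP 8.3.4 defers AE reporting to sponsor standards that are not in the documents.
- *That the call can be 2 days short.* This treats 28 to 35 as study-day numbers, whereas footnote t counts days from administration. If footnote t and 8.3.1 mean the same event, the gap is zero. If the SAP's last dose means infusion start, a call 28 days after start covers the whole TEAE window.

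**Conclusion.** The point holds as an internal conflict in the Protocol. Sections 7.1, 7.2.1 and 8.3.1 give different answers on whether a dosed participant whose infusion is stopped early stays under active AE collection, and following 7.1 as written would breach the 28-day minimum.

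The possible loss is limited to new events after the early-termination visit: up to about 28 days per such participant, or 20% of planned post-dose person-days if 1 of 5 is stopped. That figure is conditional. It assumes that a stop occurs, that it comes early enough for nearly the whole window to be lost, and that the site follows 7.1 rather than 8.3.1. The earlier healthy-participant study had no discontinuations due to AEs. Under-ascertainment of TEAEs is thus a possible consequence, not an established one.

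The unstated anchor is a minor matter of 0 to 1 day, confined to the earliest permitted call day.

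**What to change.** Reconcile 7.1, 7.2 and 7.2.1 with 8.3.1. State in 7.1 that AE/SAE collection under 8.3.1 and the 28-to-35-day call apply to every dosed participant, whatever the reason for stopping, unless consent is withdrawn. Make 7.1 and 7.2.1 agree on participants who ask to stop. This concerns data collection only and changes no rule on when treatment is stopped.

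State one anchor, the start or the end of the infusion, and use it in footnote t (with the matching text in Protocol 1.1 and 4.1), in 8.3.1 and for the last dose in SAP 6.2.

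The cost is wording in the Protocol and one clarifying phrase in the SAP, plus one phone call for each participant stopped early. The planned duration of about 11 weeks holds under either anchor (77 or 78 days).
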